## 11.2. Secondary Analysis

### Proportion of Subjects with Optimal Lens Pair

The number of lenses used for each subject will be calculated as the original pair (2) plus all the required modifications to reach the optimal pair. In this study the minimum number of lenses per subject used would be 2 where the max would be 6. The data will be dichotomized as 1 if the subject was able to achieve optimal lens pair in 4 lenses or less and 0 otherwise. The binary response will be analyzed using Bayesian logistic regression random-effects model to estimate the proportion of eyes that reached optimal lens pair in 4 lenses or less. The regression model will include strata (Hyperope and Myope), add power, age, gender, event (fitting, optimization, 2-week follow-up) and the interaction between strata by event. Site will be included in the model as a random effect. Non-informative priors will be used for the unknown parameter. For the  $\beta$  coefficients, independent non-informative priors  $N(0, 1000)$  will be used. For the variance of random effects of  $\sigma_{\text{site}}^2$  non-informative conjugate prior, inverse-gamma (0.001, 0.001) will be used. Inferences will be made based on the posterior credible interval for the relevant parameters.

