### Hypothesis Testing

With respect to the proportion of subjects that have achieved optimal fitting in 4 lenses or less, the null and alternative hypothesis for superiority is as follows:

$$H_0: p_T \leq 0.90$$

$$H_A: p_T > 0.90$$

Where,  $p_T$  represents the proportion of subjects that have achieved optimal fitting in 4 lenses or less. Success for will be declared if the lower bound of the 2-sided 95% credible interval of the proportion is greater than 0.90; i.e.  $P(p_T > 0.90) \geq .975$ .

If not enough events occur during the duration of this study the model presented for the safety population.

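### The secondary logistic model carries a three-level event factor for an outcome that exists once per subject, and neither the data layout nor the tested proportion is defined

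*SAP*

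**What the plan says.** SAP 11.2 (Proportion of Subjects with Optimal Lens Pair) builds the outcome from a per-subject total: "The number of lenses used for each subject will be calculated as the original pair (2) plus all the required modifications", with the range given as "the minimum number of lenses per subject used would be 2 where the max would be 6". It is then reduced to one binary value: "The data will be dichotomized as 1 if the subject was able to achieve optimal lens pair in 4 lenses or less".

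The model is a Bayesian logistic regression on strata, add power, age and gender, plus "event (fitting, optimization, 2-week follow-up) and the interaction between strata by event". On random effects the section says only: "Site will be included in the model as a random effect". The model's purpose is given as "to estimate the proportion of eyes that reached optimal lens pair in 4 lenses or less", whereas the Hypothesis Testing text that follows says p_T "represents the proportion of subjects that have achieved optimal fitting in 4 lenses or less". Success requires the lower limit of the two-sided 95% credible interval to exceed 0.90, that is, a posterior probability of at least 0.975.

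Protocol 14.6 describes the same model. The code in SAP Appendix 14.2 covers the primary analyses only.

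**The concern.** A factor for fitting, optimization and 2-week follow-up belongs in a model whose response can vary between those events. Here the response is a subject's final status, so it has no event level.

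Elsewhere the SAP does provide for repeated measurements. Section 11.1 specifies an unstructured within-subject covariance for CLUE vision and for visual performance, and the appendix code for visual performance includes a random subject effect. The secondary model has neither.

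The pass mark for a formal hypothesis therefore depends on choices the plan leaves open: how many rows each subject contributes, whether the response is copied or redefined at each event, and at which event, or over which average of events, p_T is read. Some of these choices make the credible interval too narrow. All of them could be made after the data are seen.

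**Working it through.** **No figure to reproduce.** The documents give no power, sample size or error rate for the secondary hypothesis. The one stated identity holds: 1 − 0.05/2 = 0.975.

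**Possible layouts**

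1. *One row per subject.* No subject belongs to a single event, so the event and strata-by-event terms cannot be fitted.
2. *The single answer copied to three rows.* The terms can be fitted, but with site as the only random effect the copies are treated as independent.
3. *A response redefined as status so far.* Protocol 7.2 allows up to two modification attempts at Visit 1 and two at Visit 2. Counting one lens per modification (an assumption, which matches the stated maximum because 2 + 2 + 2 = 6), nobody can exceed four lenses at fitting, so everyone scores 1 there. Step 3.9 allows no lens change from the Visit 3 over-refraction, so the 2-week level largely repeats optimization.

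The term is sound in none of these.

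**Inputs for the size.** N = 60 completers (SAP 3.1); null value 0.90 and pass rule P(p > 0.90 | data) ≥ 0.975 (SAP 11.2). Covariates and the site effect are left out. Subjects are the independent units, so with x successes the false-claim rate for a pass mark r is P(X ≥ r), X ~ Binomial(60, 0.90):

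| r | P(X ≥ r) |
|---|---|
| 56 | 0.271 |
| 57 | 0.137 |
| 58 | 0.053 |
| 59 | 0.014 |

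**Pass mark, N(0, 1000) prior on the logit** (intercept only, 1000 taken as a variance, as in the SAP's appendix code). The posterior for θ = logit(p) is proportional to exp(xθ)/(1 + exp θ)^n × exp(−θ²/2000).

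- One row per subject: P(p > 0.90) is 0.943 at 57/60 (fails) and 0.985 at 58/60 (passes). Pass mark 58, error 5.3%.
- Copied to three rows and pooled: 0.951 at 168/180, i.e. 56 subjects (fails), and 0.994 at 171/180, i.e. 57 subjects (passes). Pass mark 57, error 13.7%.

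**Pass mark, Jeffreys prior.** The posterior is Beta(x + 0.5, n − x + 0.5); its 2.5% quantile must exceed 0.90.

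- One row: 0.873 at 57/60, 0.897 at 58/60, 0.925 at 59/60. Pass mark 59, error 1.4%.
- Tripled and pooled: 0.890 at 168/180, 0.911 at 171/180. Pass mark 57, error 13.7%.

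**Copied rows with strata-by-event cells** (30 subjects per stratum), by where p_T is read:

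| Prior | One event | Averaged over events |
|---|---|---|
| Near-flat logit | 5.3% | 13.7% |
| Jeffreys | 1.4% | 5.3% |
| Uniform | 0.2% | 3.3% |

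Read at one event, p_T rests on 60 rows, so nothing is tripled.

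**If N = 80** (the enrolment target), over the same three priors: one row per subject gives 1.1% to 3.5%; tripled and pooled gives 8.8% to 17.7%.

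**The case against.** The strongest reply is that the documents never say the rows are copied. A reader might infer from the event factor that the model does triple the sample and inflate the error. That goes beyond the text: inflation by this route needs both copied outcomes and a p_T pooled or averaged over events, and the SAP specifies neither. With p_T read at a single event in a strata-by-event model there is none. This part of the objection stands, and the size is stated conditionally for that reason.

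A second reply concerns the contrast. Setting 1.4% against 13.7% suggests a tenfold rise, but the 1.4% depends on a Jeffreys prior. Under the prior the SAP names, the uncopied rate is already about 5.3%, so the rise is about 2.6-fold (13.7/5.3). This stands too.

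Third, SAP 11.2 ends with a fallback for too few events that points towards the safety-analysis model, which has no event factor. The sentence is incomplete and states no trigger, so it does not settle which model applies.

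Fourth, the test is reached only if all seven primary hypotheses are met, so study success is not at risk. That limits the consequence. It does not correct the interval once the secondary test is run.

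**Conclusion.** The model is mis-specified as written. The event and strata-by-event terms do not fit an outcome defined once per subject, no within-subject dependence is specified, the event at which p_T is read is not stated, and the stated unit shifts between eyes and subjects. This follows from the text and needs no numerical assumption.

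The numerical consequence is conditional. If answers are copied to three rows and pooled over events, the pass mark at N = 60 falls to 57/60 and the one-sided false-claim rate at a true 90% is about 13.7%. The comparison is about 5.3% (58/60) under a near-flat logit prior, or 1.4% (59/60) under Jeffreys, against a nominal 2.5% in the tested direction; the spread of the uncopied rates around 2.5% comes from discreteness and the prior. All figures leave out covariates and site. An unconditional claim of inflation is not supported, because a single-event reading of p_T avoids it. The issue is confined to the secondary hypothesis.

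**What to change.** Amend SAP 11.2 to use one row per subject. Remove event and the strata-by-event interaction, keep strata, add power, age and gender as fixed effects with site random, and replace eyes with subjects in the description of the fitted proportion. Protocol 14.6 has the same wording; SAP Section 1 states that the SAP prevails where the two differ, so an SAP amendment suffices.

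The cost is a wording change. The test may be stricter than under a pooled three-row layout: at N = 60 the pass mark would be 58/60 rather than 57/60 under the near-flat prior approximation. Nothing in the primary analyses changes.

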### Hypothesis Testing

With respect to the proportion of subjects that have achieved optimal fitting in 4 lenses or less, the null and alternative hypothesis for superiority is as follows:

$$H_0: p_T \leq 0.90$$

$$H_A: p_T > 0.90$$

Where,  $p_T$  represents the proportion of subjects that have achieved optimal fitting in 4 lenses or less. Success for will be declared if the lower bound of the 2-sided 95% credible interval of the proportion is greater than 0.90; i.e.  $P(p_T > 0.90) \geq .975$ .

If not enough events occur during the duration of this study the model presented for the safety population.

### **11.3. Other Analysis**

There are no other pre-planned analyses for this study.

## **12. SAFETY EVALUATION**

### **12.1. Adverse Events**

Listings of all reported ocular and non-ocular AEs and SAEs will be reported and will include lens type, eye diagnosis, severity of the AE, the number of days the subject spent in the study, the slit lamp findings at discovery of the AE, whether or not it is lens related, the possible cause, and treatments provided to the patient, the outcome, the subjects final Snellen visual acuity, whether or not the subject eye had a scar at the resolution of the AE and the action taken. In addition, the total number of subjects and the total number of eyes with each type of AE (SAEs, ocular AEs and non-ocular AEs) will be tabulated and presented as a footnote in each summary.

### **12.2. Keratometry and Over Refraction**

Keratometry will be assessed for each eye at Entrance (Visit 1) for the following metrics: (1) Steep Dioptric Power, (2) Steep Degrees, (3) Flat Dioptric Power and (4) Flat Degree. Each keratometry metric will be summarized using n, mean, min, and max across eye type and summarized by stratum (Hyperopes and Myopes) and across all subjects.

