1.13	Keratometry	Keratometry will be performed OD and OS and the steep and flat dioptic power and corresponding meridians recorded.
1.14	Subjective Refraction and Distance Visual Acuity	An optimal, binocular balanced distance spherocylindrical refraction will be performed. Record the refraction and distance visual acuity to the nearest letter. Note: Best distance visual acuity with spherocylindrical refraction must be at least 20/20³ in each eye for the subject to be eligible in the study.
1.15	Near ADD Determination	The near reading addition will be determined using the binocular crossed cylinder technique (BCC) at 40 cm followed by optimization in a trial frame in step 1.17 below.
1.16	Ocular Dominance	Determine the distance ocular dominance with the best distance correction in place using a +1.00-blur test. If the results are equivocal use the sighting dominance test to determine the dominant eye used for the study.
1.17	ADD Refinement	Place the BCC result in the trial frame and refine the near prescription with trial lenses (or flippers) under binocular conditions.

Clinical Study Protocol
Johnson & Johnson Vision Care, Inc.

1.18	Near Visual Acuity	Using the ETDRS 2000 Series Chart 1 or 2 near card placed at 40 cm. Record the near visual acuity OD, OS and OU at 40 cm.	
1.19	Biomicroscopy	
FDA Slit Lamp Classification Scale* will be used to grade the findings and determine eligibility.
 
*note: for corneal staining note location (nasal, temporal, superior, inferior or central)
 
If any of these slit lamp findings are Grade 2 or higher, the subject will be discontinued. If discontinued a final examination must be completed.
 
If the clearance of the fluorescein needs to be expedited, preservative-free rewetting drops may be instilled.
	
1.20	Eligibility after Baseline	
All responses to Inclusion Criteria questions must be answered "yes" and all responses to Exclusion Criteria questions must be answered "no" for the subject to be considered eligible.
 
If so, proceed to lens fitting. If not, complete the final evaluation and discharge the subject.
	

Visit 1: Treatment 1 Lens Fitting		
Step	Procedure	Details
1.21	Lens Selection	The lens powers (distance and ADD) will be selected based upon the calculation provided in EDC. Record the test lens parameters (power and lot number).

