Hesitates or is unsure about which is clearer.	Do not add any power but proceed to Step 5.									
4	Determine cylinder power and axis as described previously in the Cylinder Axis and Cylinder Power Determination procedure tables.									
5	Remove +1.00D from the left eye and introduce +1.00D over the right eye.									
6	Repeat Steps 3-5 for the left eye.									

7	Remove +1.00D from right eye.
8	Follow steps for Binocular Refraction Endpoint (described previously).

OCULAR DOMINANCE

The following steps are used in the determination of ocular dominance.

Step	Action	
1	Ask the subject to extend both arms out and use his/her hands to form a triangle.	
2	Ask the subject to keep both eyes open, and look through the triangle at a small object on the wall (e.g., a light switch or doorknob).	
3	Occlude the subject's left eye, then right eye.	
4	While alternating the occluder from the subject's eyes, ask the subject when they see the object.	
If the subject sees the object...		Then
When the left eye is covered		The subject is right eye dominant.
When the right eye is covered		The subject is left eye dominant.
With both eyes		The opening between the hands may be too large. Therefore, ask the subject to make a smaller opening and repeat the procedure.

GRADING SCALE

Refraction: Sphere and Cylinder Power (+20.0 to -20.0D, 0.25D increments).
Cylinder Axis (0-180°, one-degree increments).

Visual acuity should be recorded using the Snellen visual acuity descriptors on the charts. As a minimum, visual acuity should be recorded monocularly. Refer to the current revision of [CTP-2025](#) for VA recording.

ADDITIONAL INFORMATION

To minimize memorization, all available 20/20 lines on the Snellen charts should be randomly utilized when testing the patient. In addition, the patient can be asked to read the letters in a line in reverse order.

TRAINING REQUIREMENTS

The training requirement for this document is "Read only."

**Clinical Study Protocol
Johnson & Johnson Vision Care, Inc.**

CTP-2018, BIOMICROSCOPY SCALE

Title:	Biomicroscopy Scale
Document Type:	Work Instruction
Document Number:	CTP-2018
	Revision Number: 9

1.0 PURPOSE	This document contains instructions for the determination of the level of corneal edema, corneal neovascularization, corneal staining, conjunctival injection, tarsal abnormalities, and other complications in each eye.
--------------------	---

2.0 DEFINITIONS	The following definitions are provided for clarity.

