### **8.2. Summary Statistics**

Throughout the analysis of data, the results for each subject/eye will be used when available for summarization and statistical analysis. Unscheduled visits will be summarized separately and will be excluded from the efficacy statistical analysis but will be included in the analysis of safety endpoints (slit lamp findings and lens fitting).

Summary tables (descriptive statistics and/or frequency tables) will be provided for all baseline variables, efficacy variables and safety variables as appropriate. Continuous variables will be summarized with descriptive statistics (n, mean, standard deviation [SD], median, minimum, and maximum). Frequency count and percentage of subjects or eyes within each category will be provided for categorical data.

Safety and efficacy variables will be summarized on both safety and PP populations.

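### SAP 12.2 plans arithmetic means, minima and maxima of corneal meridians in degrees; these are axial data, so a printed mean can be wrong by up to 90 degrees when meridians lie near 0/180.

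*SAP*

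**What the plan says.** Protocol 7.2, Visit 1 step 1.13, has keratometry done on both eyes, with "the steep and flat dioptic power and corresponding meridians recorded". The degree values are therefore the orientations of the two principal meridians.

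SAP 12.2 names the metrics as "1) Steep Dioptric Power, (2) Steep Degrees, (3) Flat Dioptric Power and (4) Flat Degree" and gives one rule for all four: "Each keratometry metric will be summarized using n, mean, min, and max across eye type". The table is to be produced by stratum and across all subjects. Right and left eyes are pooled.

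The general rule in SAP 8.2 is no different in kind: "Continuous variables will be summarized with descriptive statistics (n, mean, standard deviation [SD], median, minimum, and maximum". Neither document names an axial mean, a vector method or orientation categories for the meridians. SAP section 1 makes the SAP the final guidance for the analysis, so a programmer who follows it will print these means.

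The keratometry procedure in Protocol Appendix H is redacted. The only degree scale that can be read is the one for refraction, in CTP-2016: "Cylinder Axis (0-180°, one-degree increments". On that scale a single direction can be entered as either 0 or 180.

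**The concern.** A mean, minimum and maximum assume that the two ends of a scale are far apart. For a meridian they coincide. Three consequences follow.

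- The mean can point in a direction that no eye has. In the worst case it is perpendicular to the true common direction.
- The mean depends on a coding choice. Re-entering one eye from 0 to 180 changes nothing about the cornea, but it moves the printed mean.
- The minimum and maximum of a sample that straddles the boundary run towards 0 and 180, and so say little about how tightly the meridians cluster.

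At stake is the correctness of up to two columns of one planned table, by stratum and overall. Keratometry is measured at Visit 1. No eligibility criterion in Protocol 3.2 and 3.3 uses a keratometry value, and keratometry enters no hypothesis, model or sample-size calculation.

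**Working it through.** The plan gives no figure to reproduce on this point. The check compares the arithmetic mean with the axial mean.

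**Formula.** For meridians θ₁ … θₙ, the axial mean is half the direction of the vector (Σ cos 2θᵢ, Σ sin 2θᵢ). The error is the gap between the two means, measured modulo 180, so it cannot exceed 90 degrees.

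**Two eyes, no assumption needed.** Take 5 and 175 degrees.
- Arithmetic mean: (5 + 175)/2 = 90.
- Doubled angles: 10 and 350. The sines cancel and the cosines add, so the vector points to 0 and the axial mean is 0, the same meridian as 180.
- Error: 90 degrees.

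**Coding.** With 60 completers there are 2 × 60 = 120 eyes. Recoding one eye from 0 to 180 moves the arithmetic mean by 180/120 = 1.5 degrees. Recoding 20 eyes moves it by 20 × 1.5 = 30 degrees. The axial mean does not move.

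**Simulation.** The documents give no meridian distribution, so every centre and spread here is an assumption. Settings: 120 eyes, 4,000 replicates, normal scatter with SD 15 degrees, values rounded to whole degrees, an exact 0 coded as 180, and the steep meridian set at flat plus 90. Entries are averages over replicates, in degrees.

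| Flat meridians centred on | Arithmetic mean, flat | Error, flat (95% range) | Error, steep |
|---|---|---|---|
| 0/180 | 92.5 | 83.2 (70.5 to 89.9) | 0.1 |
| 5 | 74.0 | 69.0 (52.6 to 85.5) | 0.1 |
| 10 | 57.3 | 47.3 (33.2 to 61.9) | 0.1 |
| 15 | 44.9 | 29.9 (18.1 to 42.4) | 0.1 |
| 20 | 37.4 | 17.5 (9.0 to 27.1) | 0.1 |
| 30 | 34.5 | 4.5 (0.1 to 10.3) | 0.1 |
| 45 | 45.3 | 0.3 (0.0 to 1.6) | 0.3 |
| 90 | 90.0 | 0.1 (0.0 to 0.4) | 83.1 |

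**Sensitivity, with flat meridians centred on 0/180:**
- Changing the SD from 10 to 20 leaves the average flat error at about 83.
- With the 60 eyes of one stratum (2 × 30 completers) and SD 15, the average is 80.6, with a 95% range of 62.9 to 89.9.
- If 20%, 30% or 50% of eyes are recorded as exactly 180, the error falls to 70, 61 or 44. Recording them as exactly 0 gives the same sizes.
- If 10% to 40% of eyes centre on 90 instead, the error is still 83 to 79.
- With 40% centred on 90 and another 20% at random, both errors average about 42, because the sample has no stable common direction.

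**What the printed table would look like.** With flat meridians at 0/180, the flat and steep means average 92.5 and 90.0. With flat meridians at 90, they average 90.0 and 92.4. These two samples have opposite orientations, yet their means are nearly the same, and in each the two perpendicular meridians appear to coincide.

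**The case against.** The strongest reply is about size and consequence, and much of it stands.

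A reader might infer that the printed flat mean will be about 90 degrees wrong for ordinary eyes. That needs flat meridians clustered symmetrically about 0/180. The documents give no distribution of corneal meridians and describe no typical eye; the nearest limit, at most 0.75 D in Protocol 3.2, concerns refractive cylinder. Nor do they say that right and left axes mirror each other, which is what would make pooled eyes symmetric about the boundary. Even under full symmetry the average error per sample is about 83 degrees, not 90, and under other centres it falls to almost nothing.

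Three further limits also stand:

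- Minimum and maximum are not uninformative in every sample. When flat meridians lie near 0/180, the steep ones lie near 90 and their range brackets 90 sensibly. An attentive reader could use that contrast to see which mean has failed.
- The amount of astigmatism is not lost. Mean steep power minus mean flat power, over the same eyes, is the mean corneal astigmatism. Only its spread and its orientation are missing.
- In the clear-cut cases only one of the four means is badly wrong. The two power means are always valid.

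None of this rescues the rule. It gives a sound mean only if the meridians happen to lie away from the boundary, and the SAP neither checks for that nor offers an alternative. The two principal meridians are perpendicular, so when one clusters well away from 0/180 the other may lie on it.

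**Conclusion.** The rule is wrong as written for the two degree metrics. That conclusion rests only on the text of SAP 12.2, the protocol's description of the degrees as meridians, and the fact that a meridian repeats every 180 degrees.

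The size is conditional. The error can reach 90 degrees when meridians lie near 0/180. Under the assumed distributions the average error in the flat mean runs from about 83 degrees (centre 0/180), through 69 to 18 degrees (centres 5 to 20), to near zero (centres 45 and 90); with flat meridians at 90 the steep mean has the error. The documents do not show which case applies, so no single figure should be quoted for this trial.

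The consequence is small: one descriptive baseline table. No study conclusion depends on it.

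**What to change.** Revise the summary sentence in SAP 12.2.

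- **Powers:** keep ordinary statistics for steep and flat dioptric power. Adding SD and median would bring the section into line with SAP 8.2.
- **Meridians:** drop the mean, minimum and maximum in degrees. Replace them, by stratum and overall, with any one of the following:
  - the axial (doubled-angle) mean, given with its resultant length so that a sample without a common direction is visible;
  - counts of with-the-rule, against-the-rule and oblique eyes, with the cut-offs stated;
  - the components J0 = (C/2) cos 2α and J45 = (C/2) sin 2α per eye, where C is steep minus flat power and α is the flat meridian. These can be averaged in the ordinary way.
- **Optional:** add corneal astigmatism per eye (steep minus flat, D) to show its spread.

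Any of the three options is adequate; the choice between them is a matter of preference. The cost is one sentence and a small change to a table shell. All the data are already collected at Visit 1.
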